6.1.6 Hepatitis Screening

Blood samples will be collected at screening from all patients in order to perform hepatitis B surface antigen and hepatitis C antibody (immunoglobulin G) testing. Test results will be sent to the screening site and must be reviewed before the Day 1 visit. Details regarding sample collection, processing, and shipping can be found in the study reference manual.

6.1.7 HIV Screening

Patients are required to provide blood samples for HIV virus types 1 and 2 testing. Test results will be sent to the screening site and must be reviewed before the Day 1 visit. Any patient who tests positive for HIV will be excluded from participating in the study. Patients will be informed of positive HIV results and referred for follow-up testing and counseling, and health authorities will be notified of positive HIV results consistent with federal, state, and local laws. Details regarding sample collection, processing, and shipping can be found in the study reference manual.

6.1.8 Urine Drug and Alcohol Screening

Urine drug (amphetamines, barbiturates, benzodiazepines, cannabinoids [THC], cocaine metabolites, methadone, opiates, phencyclidine, propoxyphene) and alcohol tests will be performed. Any patient who tests positive for any drug, excluding prescription benzodiazepines, prescription opiates, and cannabinoids, or alcohol at screening will be excluded from participating in the study. Further information regarding sample collection, processing, and shipping can be found in the study reference manual.

6.1.9 Laboratory Assessments

Laboratory assessments performed at screening are described in Section 6.4.2.9.

6.1.10 Serum and Urine Pregnancy Tests

Female patients who are of childbearing potential will undergo serum and urine pregnancy tests at the study clinic at Screening, at the Baseline Visit (Day 1), and, at the discretion of the Investigator, at an Unscheduled Visit. Serum pregnancy testing will be performed using blood collected as part of protocol-specified sample; urine pregnancy testing will use a urine dipstick.

If the urine and serum pregnancy tests at screening are positive, the patient will not be eligible to participate in the study. If a urine pregnancy test is negative and the associated serum pregnancy test is positive, the patient will be discontinued from the study. Further details regarding sample collection and processing can be found in the study reference manual.

6.1.11 Structured Clinical Interview

The major clinical criterion for inclusion in the study is that the patient be diagnosed with Bipolar I or Bipolar II Disorder, meeting the DSM-5 criteria. The methodology for confirming this diagnosis is either the SCID-5-CT, a semi-structured interview for making the major DSM-5 Axis I diagnosis ([First, 2014](#)) to be used by US sites only, or by the MINI 7.0.2 (08 August 2016 version) by [name] ([Sheehan et al, 1998](#)), to be used by non-US sites. These assessments will be used in this study at screening only to confirm the diagnosis of bipolar depression in patients evaluated for inclusion in the study. The diagnostic assessment will be completed by the Investigator or an expert site-based rater approved by the Sponsor.

[figure not shown]
6.1.12 Bipolarity Index

The Bipolarity Index (BPI) was designed to provide a measure of quantitative measure of diagnostic confidence by mapping the known information about an individual patient on 5 dimensions of illness (signs and symptoms, age of onset, course of illness, response to treatment and family history) onto a scoring hierarchy based on the presence of elements considered most characteristics of bipolar disorder. The information necessary to score the BPI can be extracted from clinical interviews, either administered by clinicians or as a self-report questionnaire. The BPI will be completed by a qualified site-based rater at the screening visit. The patient's responses to the BPI and the BPI score generated by the BPI may be reviewed by an independent expert as a component of the systematic patient adjudication process.

The BPI was developed by a group of bipolar disorder experts including Gary Sachs ([Sachs, 2004](#)). The scoring system is divided into 5 dimensions including episode characteristics, age of onset (first affective episode), course of illness/associated features, response to treatment, and family history. Each dimension is given a score of 0 to 20 based on its correlation with bipolar disorder characteristics, and the scores are added to derive the BPI score. The

maximum score is 100. The score represents how close the patient is to having bipolar disorder.

The BPI has been used to evaluate diagnostic confidence for patients entering global clinical studies. This assessment will be used by US sites only in conjunction with the SCID-5-CT.

6.1.14 Columbia Suicide Severity Rating Scale

The C-SSRS is a questionnaire developed and validated by Kelly Posner and colleagues (2011) for the assessment of suicidal ideation and behavior. Several versions have been developed including the “Baseline” and “Screening” versions and a combined “Baseline/Screening” version of the scale which assesses suicidal ideation and behavior in a patient’s lifetime and during a predefined time period. This version can assess a patient’s lifetime suicidality as well as eligibility based on inclusion/exclusion criteria. A separate “Since Last Visit” version of the scale has been developed which is used to assess suicidality since the patient’s last visit. This version is meant to assess patients who have completed at least 1 initial C-SSRS assessment and should be used in every subsequent visit. The “Since Last Visit” version of the C-SSRS addresses any suicidal thoughts or behaviors the patient/participant may have had since the last time the C-SSRS was administered.

The C-SSRS will be administered by the Investigator or an expert site-based rater, as indicated in the schedule of events (Table 6-1).

At screening, a potential study participant will not be eligible if he or she reports suicidal ideation of Type 4 or 5 on the C-SSRS within 6 months prior to screening or any suicidal behavior in the last 2 years prior to screening, as indicated by any “yes” answers on the suicidal behavior section of the C-SSRS.

6.1.15 Young Mania Rating Scale

The YMRS is an 11-item, clinician-administered mania rating scale with established reliability, validity, and sensitivity that was designed to assess the severity of manic symptoms (Young, 1978). Four of the YMRS items are rated on a 0 to 8 scale, with the remaining 7 items rated on a 0 to 4 scale. The total score is appropriate both for assessing baseline severity of manic symptoms and for assessing treatment-emergent manic symptoms in patients with Bipolar I or Bipolar II Disorder with depression. It will be completed by the Investigator or an expert site-based rater.

Note: Computer-based assessments will be utilized at sites that initiated under Version 1.3 of this protocol or prior versions. Assessments completed at sites initiated with Version 1.4 and any future versions of the protocol will be paper-based.

At each visit with a YMRS assessment, the rater-administered YMRS interviews will be audio recorded (this applies to computer-administered assessment only); at each visit after the screening visit, a computer-administered interview will also be completed by patients. Where computer-administered assessments are not being used, the assessment completed by the patient will be paper-based.

6.1.16 Clinical Global Impression Scale of Bipolar Illness—Severity of Illness

The Clinical Global Impressions Scale has been modified specifically for use in assessing global illness severity and change in patients with bipolar disorder (CGI-BP-S) (Spearing, 1997). The CGI-BP-S is a standardized assessment tool that a clinician can use to rate the severity of illness, change over time, and efficacy of medication, taking into account the patient's clinical condition and the severity of side effects. The CGI-BP-S is used to document the clinician's impression of the patient's current illness state; it will be used in this study at screening (as a criterion for inclusion or exclusion) and throughout the study as a measure of efficacy (Section 6.2.2). Scores on the CGI-BP-S range from 1 (not ill at all) to 7 (among the most extremely ill). A CGI-BP-S assessment will be completed by the Investigator or another Sponsor-approved expert site-based rater. The Depression score is based on the clinician's assessment of depression symptom severity; the Mania score is based on the clinician's assessment of mania symptom severity; and the Overall score is based on the clinician's overall impression of illness severity.

6.2 Efficacy Assessments and Procedures

6.2.1 MADRS

The MADRS is a 10-item checklist designed to measure the overall severity of depressive symptoms. Individual items are rated by the Investigator (or another Sponsor-approved expert site-based rater) on a scale of 0 to 6 in which a score of 6 represents the most severe symptoms for each item assessed. The total score ranges from 0 to 60. The MADRS is administered using a structured interview to ensure reliability and completeness. The format of the interview varies by region based on use of either Structured Interview Guide for the MADRS (SIGMA; when paper forms are used) or a similar interview structure when electronic tablets are used for scoring.

Note: Computer-based assessments will be utilized at sites that initiated under Version 1.3 of this protocol or prior versions. Assessments completed at sites initiated with Version 1.4 and any future versions of the protocol will be paper-based.

Remission of depression based on the MADRS is generally defined as a patient with a MADRS total score of ≤ 12 at endpoint. A response based on the MADRS is defined as a $\geq 50\%$ reduction from baseline in total MADRS score at endpoint.

The total score on the MADRS at screening is a major criterion for inclusion in the study, as well as the primary outcome measure for the study.

At each visit with a MADRS assessment, the rater-administered MADRS interview will be audio recorded (note: audio-recording applies to computer-based assessments only). At each

visit after screening, computer-administered MADRS interview will also be completed by patients. The computer-administered interview will involve a series of probe and follow-up questions with multiple-choice response options. Where paper scales are used, the SIGMA will be used to collect data for scoring MADRS.

6.2.2 Clinical Global Impression of Bipolar Illness–Severity

The CGI-BP-S, described in Section 6.1.16, will be a clinical efficacy assessment by the Investigator of each patient's severity of illness. The Clinical Global Impression Scale is a widely accepted measure of illness severity in a variety of psychiatric disorders. The CGI-BP-S will be assessed at Baseline/Visit 2, Visits 3-8, and Visit 9/ET. Details related to the statistical analysis of the CGI-BP-S scores are provided in Sections 7.5.5 and 7.5.6.

6.2.3 Sheehan Disability Scale

The SDS is a validated patient self-reported measure of psychosocial disability. It is widely used in many chronic mental illnesses because of its generic design. The SDS consists of 3 subscales for the items "Work/School," "Social Life," and "Family Life/Home Responsibilities." Each subscale consists of a visual analog scale on which the patient scores each item from 0 ("not at all") to 10 ("extremely") in response to each question of how much each subscale aspect is impaired. Changes in the score for each item are evaluated to assess the change in severity of each domain. The scores may also be summed across the 3 subscales to assess overall change in disability. Note: This scale is to be administered to US patients only.

6.2.4 Quality of Life Enjoyment and Satisfaction Questionnaire – Short Form

The Q-LES-Q-SF is a patient self-reported questionnaire that assesses how satisfied a patient is, using a 5-point rating scale from very poor to very good, with 14 items. The items assessed include physical health, mood, work, household activities, social relationships, family relationships, leisure time activities, ability to function in daily life, sexual drive/interest/performance, economic status, living/housing situation, ability to get around physically without feeling dizzy or unsteady or falling, vision in terms of ability to do work or hobbies, and overall sense of well-being that are summed to provide a raw total score ranging from 14 to 70. here are an additional 2 stand-alone items (1 for medication

satisfaction and the other for overall life satisfaction). The total raw score is converted to a percent score.

6.2.5 World Health Organization-5 Well-Being Index

The WHO-5 is a patient-reported outcome measure developed by the World Health Organization. This self-reported questionnaire consists of 5 questions regarding subjective quality of life based on positive mood, vitality, and general interest, each rated on a 6-point Likert scale from 0 (at no time) to 5 (all the time). The sum of scores represents the raw scores with 0 representing the worst possible quality of life and 25 representing the best possible quality of life. A score below 13 represents poor well-being. To calculate the percentage score, the raw score is multiplied by 4, with 100% representing the best possible quality of life. A 10% difference over time indicates a meaningful change. The WHO-5 has been found to have adequate validity as an outcome measure in clinical studies (Topp, 2015).

Note: This scale is to be administered to US patients only.

6.2.6 Neuroticism, Extraversion, and Openness to Experience-Five Factor Inventory

The NEO-FFI is a 60-item self-report scale (Costa, 1992). Each item is rated on a 5-point scale. Twelve items assess each of 5 dimensions of personality: neuroticism (N), extraversion (E), conscientiousness (C), openness (O), and agreeableness (A). Note: This scale is to be administered to US patients only.

6.3 Patient Placebo-Response Training

A brief training explaining the use of placebo in this study will be provided to all patients at Baseline (Visit 2). In addition, site staff will receive a brief training defining the placebo response in clinical drug trials. Completion of placebo-response training will be documented for both patient and site staff.

6.4 Safety and Tolerability Assessments

All patients who receive study medication will be evaluated for safety. Safety assessments will include incidence of AEs; suicidality assessment by the C-SSRS; mania assessment by the YMRS; movement disorder assessment by the AIMS, BARS and SAS; clinical laboratory evaluations; ECG evaluations; vital sign measurements; and physical and neurological examinations.

6.4.1 Adverse Events

The Investigator is responsible for reporting all AEs that are observed or reported during the study, regardless of their relationship to study medication or their clinical significance.

6.4.1.1 Definition of Adverse Event

An AE is any untoward medical occurrence in a study patient administered a study medication, whether or not considered drug related. This can be any unfavorable and unintended sign (such as an abnormal laboratory finding), symptom, or disease temporally associated with the use of a study medication, without any judgment of causality.

The AE may be:

- A new illness;
- A worsening sign or symptom of the condition under treatment, or of a concomitant illness;
- An effect of the study medication, including comparator; or
- A combination of 2 or more of these factors.

No causal relationship with the study medication or with the clinical study itself is implied by the use of the term AE.

Surgical procedures themselves are not AEs; they are therapeutic measures for conditions that require surgery. The condition for which the surgery is required may be an AE. Planned surgical measures, if permitted by the clinical study protocol and the conditions leading to those measures are not AEs.

All AEs fall into the categories of “nonserious” or “serious” (Sections 6.4.1.2 and 6.4.1.3).

Any abnormal laboratory test results (hematology, clinical chemistry, or urinalysis) or other safety assessments (eg, ECGs, vital sign measurements), including those that worsen from baseline, felt to be clinically significant, in the medical and scientific judgment of the investigator, are to be recorded as AEs or SAEs.

However, any clinically significant safety assessments that are associated with the underlying disease, unless judged by the investigator to be more severe than expected for the patient's condition, are not to be reported as AEs or SAEs.

6.4.1.2 Definition of Serious Adverse Event

An SAE is defined as any untoward medical occurrence that at any dose:

- Results in death;
- Is life threatening;
- Requires hospitalization or prolongation in existing hospitalization;
- Results in persistent or significant disability or incapacity; or
- Is a congenital anomaly or birth defect.

The term "life threatening" refers to an event in which the patient is at risk of death at the time of the event; it does not refer to an event, which hypothetically might have caused death if it were more severe.

Medical and scientific judgment should be exercised in deciding whether an AE is serious. Some important medical events that may not result in death, be life threatening, or require hospitalization may be considered SAEs when they may jeopardize the patient such that medical or surgical intervention is needed to prevent 1 of the outcomes previously listed. Examples of such medical events include intensive emergency treatment for an allergic reaction, blood dyscrasias or convulsions that do not result in inpatient hospitalization, and the development of drug dependency or drug abuse.

If either the Sponsor or Investigator believes that any event is serious, the event must be considered and evaluated by the Sponsor for possible expedited reporting.

Clarification of the difference between "serious" and "severe":

The term "severe" is often used to describe the intensity (severity) of a specific event (as in mild, moderate, or severe myocardial infarction); the event itself, however, may be of relatively minor medical significance (such as a severe headache). This is not the same as

“serious,” which is based on patient/event outcome or action criteria usually associated with events that pose a threat to a patient’s life or functioning. Seriousness (not severity) serves as a guide for defining regulatory reporting obligations.

6.4.1.3 Nonserious Adverse Event

A nonserious AE is any AE not meeting the SAE criteria.

6.4.1.4 Definition of Relationship to Study Medication

By definition, any AE that starts before the first dose of study medication administration is considered to be “unrelated.”

The Investigator will assess the causality/relationship between the study medication and the AE (Table 6-2). One of the following categories should be selected based on medical judgment, considering the following definitions and all contributing factors.

Table 6-2 **Causality Categories**

Category	Definition
Definitely related	A clinical event, including laboratory test abnormality, occurs in a plausible time relationship to treatment administration, and which concurrent disease or other drugs or chemicals cannot explain. The response to withdrawal of the treatment (dechallenge ¹) should be clinically plausible. The event must be definitive pharmacologically or phenomenologically, using a satisfactory rechallenge ² procedure if necessary.
Probably related	A clinical event, including laboratory test abnormality, with a reasonable time sequence to administration of the treatment, unlikely to be attributed to concurrent disease or other drugs or chemicals, and which follows a clinically reasonable response on withdrawal (dechallenge). Rechallenge information is not required to fulfill this definition.
Possibly related	A clinical event, including laboratory test abnormality, with a reasonable time sequence to administration of the treatment, but which could also be explained by concurrent disease or other drugs or chemicals. Information on-treatment withdrawal may be lacking or unclear.
Unlikely to be related	A clinical event, including laboratory test abnormality, with a temporal relationship to treatment administration which makes a causal relationship improbable, and in which other drugs, chemicals or underlying disease provide plausible explanations.
Unrelated	A clinical event, including laboratory test abnormality, with little or no temporal relationship with treatment administration. May have negative dechallenge and rechallenge information. Typically, explained by extraneous factors (eg, concomitant disease, environmental factors, or other drugs or chemicals).

¹ Dechallenge is when a drug suspected of causing an adverse event (AE) is discontinued. If the symptoms of the AE disappear partially or completely, within a reasonable time from drug discontinuation, this is termed a positive dechallenge. If the symptoms continue despite withdrawal of the drug, this is termed a negative dechallenge. Note that there are exceptions when an AE does not disappear upon discontinuation of the drug, yet drug-relatedness clearly exists (eg, bone marrow suppression, fixed drug eruptions, tardive dyskinesia).

² Rechallenge is when a drug suspected of causing an AE in a specific patient in the past is readministered to that patient. If the AE recurs upon exposure, this is termed a positive rechallenge. If the AE does not recur, this is termed a negative rechallenge.

6.4.1.5 Definition of Intensity

The Investigator will assess all AEs for intensity (severity) in accordance with the following standard ratings (Table 6-3):

Table 6-3 **Intensity Categories**

Category	Definition
Mild	Ordinarily transient symptoms; does not influence performance of patient's daily activities. Treatment is not ordinarily indicated.
Moderate	Marked symptoms, sufficient to make the patient uncomfortable. Moderate influence on performance of patient's daily activities. Treatment may be necessary.
Severe	Symptoms cause considerable discomfort. Substantial influence on patient's daily activities. May be unable to continue in the study and treatment may be necessary.
Life threatening	Extreme limitation in activity, significant assistance required; significant medical intervention/therapy required, hospitalization or hospice care probable.

When changes in the intensity of an AE occur more frequently than once a day, the maximum intensity for the event should be noted for that day. Any change in intensity of signs and symptoms over a number of days will be captured by recording a new AE, with the amended intensity grade and the date (and time, if known) of the change.

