6.4.1.6 Period of Observation for Adverse Events

For the purposes of this study, the period of observation extends from the time the patient gives his study-specific informed consent until the end-of-study procedures are completed.

If the Investigator detects an SAE in a study patient after the end of the period of observation and considers the event possibly related to prior study treatment, he or she should contact the Sponsor to determine how the AE should be documented and reported.

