16.1. ADVERSE EVENTS

Adverse Events (AEs) will be coded using MedDRA central coding dictionary currently in effect at the time of final database lock.

Treatment emergent adverse events (TEAEs) are defined as AEs that started or worsened in severity on or after the date of the first dose of study medication and on or before the date of last dose of study medication plus one day. Consecutive AEs with the same Preferred term and differing severity will be assessed. AEs are considered to be consecutive if the end date of the initial AE and the start date of the following AE are at most 1 day apart. If the severity of later AE stays the same or decreases after the first dose of study medication, then it will not be considered treatment emergent.

All AEs with an onset date after the last dose of study medication plus one day will be listed in the AE data listing and labelled as 'Follow-up Adverse Event'.

See Appendix 2 for handling of partial or completely missing dates for AEs. In the case where it is not possible to define an AE as treatment emergent or not, the AE will be classified as the worst case, i.e., treatment emergent.

An overall summary of the number of patients within each of the categories described in the sub-sections 16.1.1 and 16.1.2 below will be provided as specified in the TLF shells.

Listings will include all adverse events, TEAEs and Non-TEAEs.

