16.1.1. AEs AND TEAEs

The incidence of TEAEs will be presented by SOC and PT and also broken down further by maximum severity and relationship to study medication.

The number and percentage of patients with at least one TEAE and total number of patients having events for each PT and SOC will be summarized. A summary of TEAEs will be provided with only PTs and a separate summary for only SOCs. An additional summary of TEAEs will be provided for PTs occurring in at least 5% of patients in any treatment group (ITI-007 60 mg, ITI-007 40 mg, or placebo). This summary will be repeated for TEAEs related (possibly, probably, or definitely) to study drug. Within each patient, multiple reports of events that map to a common MedDRA PT and/or SOC will be condensed into a single AE for incidence counts. Summaries will be presented by treatment group and in decreasing frequency by decreasing dose group (ITI-007 60 mg, ITI-007 40 mg) and placebo group. AEs which occur during the follow-up period will be summarized by PT and SOC and treatment group.

The relative risk of at least one TEAE and for each PT and SOC will also be presented along with 95% CIs and p-values obtained by the Chi-square test for association.

Intensity is classed as “mild”, “moderate”, “severe”, or “life-threatening” (increasing severity). AEs and TEAEs with a missing severity will be classified as “not specified”. If a patient reports a TEAE more than once within the same PT and SOC, the event with the worst case severity will be used in the corresponding severity summaries.

Relationship, as indicated by the Investigator, is classed as “unrelated”, “unlikely to be related”, “possibly related”, “probably related”, or “definitely related” (increasing severity of relationship). A “related” TEAE is defined as a TEAE with a relationship to study medication as “possibly related”, “probably related”, or “definitely related” to study medication. TEAEs with a missing relationship to study medication will be classified as “related”. If a patient reports the same AE more than once within the same PT and SOC, the AE with the worst case relationship to study medication will be used in the corresponding relationship summaries. A summary of related TEAEs by SOC and PT will be presented.

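### An on-treatment adverse event that merely eases after the last dose is tabulated as a follow-up adverse event, because each grade change opens a new record and the SAP assigns follow-up status on onset date alone

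*Protocol*

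**What the plan says.** Protocol 6.4.1.5 (Definition of Intensity) sets the recording rule: "Any change in intensity of signs and symptoms over a number of days will be captured by recording a new AE". The new record takes the changed grade and the day on which it changed. The rule does not separate easing from worsening. Its one exception is for several changes within a day, where "the maximum intensity for the event should be noted for that day". Protocol 6.4.1.6 extends AE observation "until the end-of-study procedures are completed", so the roughly two weeks after the last dose are covered.

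SAP 16.1 (Adverse Events) ends the treatment-emergent window at events that started or worsened "on or before the date of last dose of study medication plus one day". It then says: "All AEs with an onset date after the last dose of study medication plus one day will be listed in the AE data listing". Such events are "labelled as 'Follow-up Adverse Event". Onset date is the only criterion given. SAP 16.1.1 adds a table: "AEs which occur during the follow-up period will be summarized by PT and SOC and treatment group".

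SAP 16.1 also has a rule for consecutive records, meaning the same PT with the end of one and the start of the next no more than one day apart. If the later record has the same or lower severity, it is not counted as treatment emergent. The rule does not merge the records and does not mention follow-up status.

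**The concern.** A follow-up AE table is normally read as showing what appeared or got worse once the drug was stopped. Here the recording rule and the labelling rule together place part of the recovery from on-treatment events in that table. The protocol's own causality notes (6.4.1.4, Table 6-2) count partial disappearance of symptoms after stopping the drug as a positive dechallenge. Under the SAP that same partial recovery can generate a post-treatment event.

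The misplacement need not be even across arms. It depends on how many patients carry a moderate-or-worse AE past the last dose, so an arm with more such events collects more of these records.

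**Working it through.** The documents give no figure to reproduce. The check applies the rules to an illustrative patient.

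**Inputs.** New record at each grade change, dated at the change (Protocol 6.4.1.5). Treatment-emergent window to last dose + 1 day, the consecutive-record rule, and the follow-up label if onset is later than last dose + 1 day (all SAP 16.1). Assumption: last dose on Day 42, so the boundary is 42 + 1 = Day 43.

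**Case 1: severe AE from Day 30 that eases to mild and continues to Day 55.**

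| Day of easing | Second record consecutive? | Second record a TEAE? | Second record a follow-up AE? |
|---|---|---|---|
| 40 to 43 | yes | no | no |
| 44 to 49 | yes | no | yes |

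In every row the Day 30 record is already a TEAE. The only thing that changes the second record's status is whether the grade drop falls before or after the Day 43 boundary.

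**Case 2: severe AE from Day 30 that stays severe and resolves on Day 47.** There is one record, a TEAE, and no follow-up AE.

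Comparing the two cases, an event that eases on Day 44 is a follow-up AE and an event that remains severe until Day 47 is not. Follow-up status therefore turns on whether the grade changed, not on whether anything new began.

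**Case 3: two steps down.** Severe on Days 30–43, moderate on Days 44–47, mild from Day 48. Both later records start after Day 43 and are labelled follow-up. The immediate predecessor of the Day 48 record itself starts in follow-up. A remedy that looks only one record back for an on-treatment start would catch Day 44 and miss Day 48, so the link has to run through the whole chain.

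**Which events can contribute.** A mild event has no lower grade to step to, so it adds nothing by easing. The event must be moderate or worse, ongoing past the last dose, and must ease without resolving on last dose + 2 days or later.

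**Size.** Affected patients per arm = N × (share with an AE ongoing at last dose) × (share of those that step down in the follow-up window). Only N = 173 (SAP 4.1) is in the documents. Purely assumed values, with the placebo share set at half the active share:

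- 10% and 1/3: 173 × 0.10 / 3 = 6 vs 3 patients
- 20% and 1/2: 173 × 0.20 / 2 = 17 vs 9
- 30% and 2/3: 173 × 0.30 × 2/3 = 35 vs 17

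The spread shows that the result is set by the assumptions. The last line also requires at least two thirds of all ongoing AEs to be moderate or worse, so it is an extreme. These counts pool all terms, and any single PT would show far fewer.

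**The case against.** The strongest reply is that little hangs on this. The on-treatment record already counts, so TEAE incidence does not move. The affected table is descriptive. Counting within a patient is condensed by PT and SOC. The listings hold every record, so an apparent excess can be traced. Few records can qualify, since after the last dose there is essentially the Day 43 visit and one safety visit about two weeks later, and AEs are volunteered or elicited by an open question. All of that stands and limits the size. Condensing, however, does not remove a patient whose only follow-up record is an eased TEAE.

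A second reply is that an event still present after the last dose does in a sense occur in follow-up. But then an event persisting at the same grade should be counted too, and under the onset-date label it is not. The rule is inconsistent on either reading.

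A third is that the table shells, Appendix 2 and much of the later SAP cannot be read, and a continuation rule might sit there. That is possible. The readable text of 16.1 nevertheless states an onset-only rule for all such AEs, without exception.

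A reader might also infer that the rule would produce a statistically significant false withdrawal or rebound signal. The documents do not support that. They give no AE rates, the readable text defines no withdrawal or rebound endpoint, and the relative risks and chi-square p-values in 16.1.1 are specified for TEAEs, with none visibly planned for the follow-up summary.

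**Conclusion.** The point holds as a misclassification in one safety summary. Read together, Protocol 6.4.1.5 and SAP 16.1 and 16.1.1 tabulate a moderate-or-worse on-treatment AE that eases, without resolving, 2 or more days after the last dose as a follow-up AE. The SAP already treats a milder consecutive record as not new for treatment emergence but does not carry that logic past last dose plus one day.

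The effect is confined to the follow-up label and the descriptive follow-up summary. It would be larger in an arm with more moderate-or-worse AEs ongoing at last dose. How large, and whether the arms differ at all, cannot be derived from the documents. It would also go too far to say that every intensity change creates a record, because several changes within a day are noted once at the maximum. The conclusion assumes that the table in 16.1.1 uses the label defined in 16.1, and that no unreadable part of the SAP overrides it.

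**What to change.** In SAP 16.1, define a follow-up AE as one that starts or worsens in severity after last dose plus one day. Add that a record is listed as continuing, and left out of the follow-up AE summary, when both of these hold:

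- it is linked through an unbroken chain of consecutive records (same PT, gap of at most one day, the SAP's existing definition) to a record starting on or before last dose plus one day; and
- its severity is the same as or lower than that of its immediate predecessor.

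In Case 3 above, both the Day 44 and Day 48 records become continuing. A record in the chain that is worse than its predecessor still counts as a follow-up AE.

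The cost is a short SAP addition and minor programming that reuses the consecutive-record derivation. No new data are needed and nothing leaves the listings. The downside is slightly lower follow-up AE counts.
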